## Secondary outcomes and analyses

The secondary outcomes are summarized in a SPIRIT figure [1].

Dichotomous secondary outcomes include:

- Delirium
  - o CAM-ICU score, ICDSC-score or DOSS-score (yes or no)
- ICU-acquired weakness
  - o Medical Research Council sum score (yes: <48, no: 48-60)
- Need for renal replacement therapy (yes or no)
- At day-28 and day-180:
  - o Survival (yes or no)

Dichotomous variables will be presented as numbers with percentages. For dichotomous variables logistic regression analyses will be carried out. Results will be presented with odds ratios and 95% confidence intervals.

Ordinal secondary outcomes include:

- Renal
  - o Calcium oxalate crystals in urine (negative, few or many)
- At day-28 and day-180:
  - o Functional outcome (mRS scale 0-6)
  - o Neurological outcome (CPC scale 0-5)

Ordinal variables will be presented as numbers with percentages. For ordinal variables a multinomial logistic regression analysis will be carried out. Results will be presented with odds ratios and 95% confidence intervals.

Continuous secondary outcomes include:

- Organ failure:
  - o SOFA-score
- Neurological:
  - o Glasgow Coma Scale
  - Neuron-specific enolase (NSE) ng/mL
  - o The Health Utilities Index-3
- Cardiac/hemodynamics:
  - $\circ$  Troponin ng/L
  - $\circ$  CK U/L
  - $\circ$  CK-MB  $\mu$ g/L
  - Vasopressor duration hours
  - Vasopressor-free days
- Lung:
  - Lung injury score
  - Ventilation duration days
  - Ventilator-free days
- Renal
  - Creatinine clearance μmol/L
  - Oxalic acid (urine) mmol/24h

- Inflammation
  - C-reactive protein mg/L
- Oxidative stress
  - Oxidation-reduction potential (ORP) mV
  - o Antioxidant capacity (AOC)  $\mu$ C
- Pharmacokinetics
  - O Plasma vitamin C concentration μmol/L
- Other clinical outcomes
  - o ICU-stay days
  - Hospital stay days

Continuous variables will be presented as mean with standard deviation or as median with interquartile range when appropriate. Q-Q plots will be assessed visually to check if a given variable follows a normal distribution. For continuous variables linear regression analyses or linear mixed model analyses will be carried out when appropriate. Results will be presented with effect sizes estimates and 95% confidence intervals. When the residuals are not normality distributed the outcome will be transformed before analysis. Analyses will be adjusted for baseline values if applicable.

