Secondary analyses will be performed crude. In an additional analysis, vitamin C groups will be combined and compared to placebo as well to estimate the overall effect of vitamin C.

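### ICU and hospital stay (and raw ventilation and vasopressor durations) are compared by linear models with no stated rule for patients who die, so the comparison may favour an arm with more early deaths

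*SAP*

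**What the plan says.** In Section 6 of the SAP, under Secondary outcomes and analyses, the continuous outcomes include ICU stay, "Hospital stay days", "Ventilation duration days" and "Vasopressor duration hours". The same list contains "Ventilator-free days" and "Vasopressor-free days". ICU and hospital stay have no counterpart of that kind.

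The method for every continuous outcome is the same: "For continuous variables linear regression analyses or linear mixed model analyses will be carried out when appropriate". The one stated fallback is "When the residuals are not normality distributed the outcome will be transformed before analysis". The section closes with "Secondary analyses will be performed crude", so no covariate adjustment is planned beyond the baseline value where one applies.

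Death is handled explicitly for the primary outcome only. Planned sensitivity analyses explains that a death by 96 h receives the maximum score of 24, acknowledges that this choice may matter a great deal, and adds an analysis without those deaths. The Missing data section deals with transfer to another hospital, failure to reach patients by phone, and tests that some ICUs do not perform routinely. It does not say what value a duration takes in a patient who dies.

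**The concern.** Death ends an ICU stay, a hospital stay, a period of ventilation and a period of vasopressor use. If the recorded duration simply stops at death, a patient who dies on day 2 contributes a short stay, and a linear model reads that as a good result. A treatment that prevented early deaths could then appear to lengthen stay, and one that caused them could appear to shorten it.

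This could matter here because early deaths are to be expected: the Background describes high mortality after cardiac arrest. A mortality difference is also something the trial itself looks for, since survival at days 28 and 180 is compared between arms and the interim analysis examines mortality by group.

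The qualifier in the method sentence chooses between two linear models and opens no route to a method that accommodates death. A transformation changes the shape of the distribution, not the meaning of a duration cut short by death.

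**Working it through.** The SAP gives no figure to reproduce on this point: no mortality rate, no length of stay and no time to death. Everything below is therefore an illustration under assumed inputs, except the arm size of 90, which is in the SAP's definition of the modified intention-to-treat population.

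**1. Size of the artefact.** Let p be the proportion who die in an arm, S the mean stay of survivors and D the mean stay of patients who die, with S and D the same in both arms. The mean stay in an arm is p × D + (1 − p) × S. For arms A and B:

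mean(B) − mean(A) = (p_A − p_B) × (S − D)

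Assume p_A = 0.40 and p_B = 0.30.

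| Outcome | D (days) | S (days) | Mean A | Mean B | B − A |
|---|---|---|---|---|---|
| ICU stay, lower | 4 | 8 | 0.4×4 + 0.6×8 = 6.4 | 0.3×4 + 0.7×8 = 6.8 | 0.10×4 = 0.4 |
| ICU stay, upper | 4 | 12 | 0.4×4 + 0.6×12 = 8.8 | 0.3×4 + 0.7×12 = 9.6 | 0.10×8 = 0.8 |
| Hospital stay | 5 | 20 | 0.4×5 + 0.6×20 = 14.0 | 0.3×5 + 0.7×20 = 15.5 | 0.10×15 = 1.5 |

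Arm B has the lower mortality and looks 0.4 to 1.5 days worse, although survivors stay equally long in both arms and patients who die do so equally early.

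**2. When it vanishes or reverses.** If p_A = p_B, and D is the same in both arms, the difference is zero. If S − D is negative, because patients who die spend longer on support than survivors do, the sign reverses. The direction therefore depends on S exceeding D, which the SAP does not establish.

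**3. Effect on the test.** A simulation used 90 patients per arm and 4,000 trials per setting. Time to live discharge was log-normal and identical in both arms (assumed median 5 days, log-SD 0.8). A stated fraction of each arm was exposed to death at an exponential time with assumed mean 2, 3 or 5 days. Recorded stay was the earlier of discharge and death. Arms were compared at two-sided 0.05, so the nominal rate in one direction is 2.5%. The ranges run over the three assumed mean times to death.

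| Fraction exposed to death | Mean stay, higher-mortality arm (raw days) | Declared significantly shorter, raw | Declared significantly shorter, log |
|---|---|---|---|
| 40% vs 40% | no difference (−0.02 to 0.01) | 2.2% to 2.5% | 2.5% to 2.7% |
| 30% vs 40% | 0.4 to 0.5 shorter | 6% to 9% | 9% to 13% |
| 30% vs 50% | 0.7 to 1.0 shorter | 16% to 23% | 21% to 40% |

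In the second row the implied gap S − D is 0.38/0.10 = 3.8 to 0.54/0.10 = 5.4 days, close to the lower end of the range in step 1. The log transformation, a natural choice under the SAP's fallback, raised the rate of misleading results in these unequal-mortality settings.

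Two cautions apply. The fractions are of patients exposed to death; some are discharged first, so deaths during the stay are somewhat fewer. And because death in this set-up can only shorten stay, the simulation shows how large the effect might be but cannot confirm its direction.

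**The case against.** The strongest reply is that the SAP does not say that deaths enter these durations unmodified. It refers to the published protocol for a summary of the secondary outcomes, and definitions may stand there, including how death counts in the free-day outcomes. That stands in part: the fair statement is that this SAP gives no rule for death, not that it prescribes a wrong one. The choice of a linear model, however, is made in the SAP and belongs there.

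A reader might infer that the plan will give a wrong-direction result whenever mortality differs. The document does not support that. The direction requires patients who die to have shorter durations than survivors. Patients enter with a Glasgow Coma Scale of 8 or less, so a survivor who wakes early could be ventilated for less time than a patient who remains comatose and dies later. The direction is most plausible for hospital stay and least secure for ventilation and vasopressor duration. A true effect on stay could also outweigh the artefact.

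A reader might also conclude that all four comparisons are uninterpretable. That goes too far. Two of the four have free-day companions, and survival is reported separately, so a mortality imbalance would be visible beside the durations. The main gap is ICU and hospital stay.

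**Conclusion.** The point holds in limited form. The SAP assigns linear models to ICU and hospital stay, and to raw ventilation and vasopressor duration, without stating how death is handled. Where deaths come early and mortality differs between arms, these comparisons may be biased in favour of the arm with more early deaths. For a 10-point mortality difference the artefact is about 0.4 to 1.5 days, if survivors stay 4 to 15 days longer than patients who die. Both inputs are assumptions. The outcomes are secondary and the primary analysis has its own rule for death, so the trial's main conclusion is untouched. The change should be made, but it is not critical to the trial's validity.

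**What to change.** For ICU and hospital stay, replace the linear model of raw days with a competing-risk analysis of discharge alive: cumulative incidence by arm with death as the competing event, and patients censored at transfer to another hospital where later data are missing. Alternatively, compare days alive and out of ICU or hospital up to a fixed, stated horizon, where the data allow.

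For ventilation and vasopressors, make the already listed ventilator-free and vasopressor-free days the compared outcomes, and state in the SAP that death counts as zero free days. Report all raw durations descriptively, separately for survivors and non-survivors. Record the change before the treatment codes are broken.

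The cost is SAP wording and modest programming, with two real drawbacks. The composites mix survival with stay, so they should be read beside the survival results. Data are also incomplete: the SAP's Follow-up and Missing data sections say that most secondary endpoints are missing after transfer. Days alive and out of hospital may therefore not be computable for transferred patients, and censoring at transfer assumes that transfer is unrelated to later outcome. The number of patients transferred should be reported by arm.

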#### Randomization

Eligible patients will be randomized using a computer-generated randomization list in a 1:1:1 ratio to one of the three treatment groups. Randomization will be stratified by site and age ( $\leq$ 66 and  $\geq$ 66 years) in blocks of 6. Patients were randomized only if early administration of the first dose ( $\leq$ 5 hours after ROSC) was still feasible. Deferred informed consent was obtained  $\leq$ 72 hours after inclusion/randomization.

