## Timing of final analysis

The final analysis for the primary and secondary endpoints is planned when the 180-day follow-up is completed for the last patient included.

The full dataset will be assessed for correctness and completeness of the data by reviewing all individual records in Castor. Any errors, discrepant or missing data will be queried and resolved. Thereafter, the database will be locked and exported for statistical analyses. First, the analyses will be performed with blinded data, i.e. included patients will be assigned to intervention A, B or C. Conclusions about the primary outcome will be drawn according to the blinded results and reported in short (abstract) format. This blinded abstract will be included as supplementary material in the paper in which the main results will be presented.

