# **Section 6: Analysis**

#### **Primary outcome and analyses**

The primary outcome is the delta 96 h resuscitation-sequential organ failure assessment score (ΔR-SOFA96-baseline): The R-SOFA score at 96 h after randomization minus the score after ROSC (baseline R-SOFA score). Our primary outcome has been described in detail in our published protocol [1]. All relevant data for the primary outcome was collected for all included patients according to the protocol. When included patients were transferred to another ICU prior to T96 h, data was retrieved from the involved hospitals (with consent).

The difference in  $\Delta R$ -SOFA96-baseline score between intervention and control groups will be analyzed using linear mixed model analyses, with a random intercept on site level. The analysis will be adjusted for the baseline SOFA-score. When the residuals are not normally distributed the outcome will be transformed before analysis.

Analysis will be performed crude and adjusting for *age* (stratification variable). This age adjusted analysis will be the primary analysis.

In additional analyses, the model will be adjusted for relevant covariates such as delay (time of no flow), total duration of CPR (time of low flow) and first measured pH [2]. Moreover, vitamin C groups will be combined and compared to placebo as well to estimate the overall effect of vitamin C.

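### Secondary analyses are fixed as crude although randomisation was stratified by site and age and the primary model uses both: valid, but slightly conservative (minor)

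*SAP*

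**What the plan says.** The SAP, Randomization, says "Randomization will be stratified by site and age", with 1:1:1 allocation in blocks of 6. Six ICUs and two age classes make 12 strata.

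Under Primary outcome and analyses the model is a linear mixed model "with a random intercept on site level", adjusted for the baseline score. The section continues "Analysis will be performed crude and adjusting for" age, which it identifies as a stratification variable, and then settles the choice: "This age adjusted analysis will be the primary analysis".

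Under Secondary outcomes and analyses the rule is different: "Secondary analyses will be performed crude". The only additional secondary analysis named there pools the vitamin C groups against placebo. The model statements are "For dichotomous variables logistic regression analyses will be carried out" and "For ordinal variables a multinomial logistic regression analysis will be carried out"; neither names a covariate or a site term. Continuous outcomes get a linear or a linear mixed model, whichever suits, and are adjusted for their own baseline value where that applies. The random effect in such a mixed model is not named.

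**The concern.** Stratified randomisation balances the arms on site and age. If those factors predict the outcome, the treatment estimate varies less from trial to trial than it would under simple randomisation. A model without the factors does not know this: it puts their variance into the residual and reports a standard error larger than the true spread. The primary analysis takes account of the design. The secondary analyses, which include survival, delirium, ventilator-free days and length of stay, drop age. They also drop site in the logistic and multinomial models, and no adjusted analysis is planned even as support. At stake are slightly wide 95% intervals and a small loss of power on secondary outcomes, in exchange for no evident benefit.

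**Working it through.** **Inputs from the SAP.** 270 patients, 90 per arm; three arms; six sites; two age classes; blocks of 6; 95% two-sided intervals. The SAP states no power for any secondary outcome, so there is no figure of its own to reproduce. The 82 per group belongs to the primary outcome. It implies an SD of 2 × √(82/2) / (2.576 + 1.282) = 3.32 and does not bear on this point.

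**Inputs assumed.** Share R² of outcome variance explained by the strata: 1, 5, 10 or 20%. Age odds ratio for binary outcomes: 1.5, 2, 3 or 5. Site shares 32/22/16/12/10/8%; 45% of patients in the older stratum; site SD 0.2 on the logit scale; treatment odds ratio 0.42 with placebo risk 40%.

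**Continuous outcomes, closed form.** Let the total SD be 1 and the effect 0.42 SD.
- Crude standard error: s = √(2/90) = 0.149, so 0.42/s = 2.817.
- True spread of the estimate under stratified allocation: s√(1−R²).
- Adjusted power: Φ(2.817/√(1−R²) − 1.96).
- Crude power: Φ((2.817 − 1.96)/√(1−R²)).
- Crude type I error: 2[1 − Φ(1.96/√(1−R²))].

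| R² | Adjusted power | Crude power | Loss, closed form | Loss, simulated | Crude type I error, closed form / simulated |
|---|---|---|---|---|---|
| 1% | 80.8% | 80.6% | 0.3 | 0.4 | 4.9 / 5.1% |
| 5% | 82.4% | 81.0% | 1.4 | 1.3 | 4.4 / 4.9% |
| 10% | 84.4% | 81.7% | 2.7 | 2.6 | 3.9 / 4.2% |
| 20% | 88.3% | 83.1% | 5.2 | 5.4 | 2.8 / 2.9% |

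The simulation used 16,000 trials per scenario, permuted blocks within site by age, and a random intercept for site. The adjusted standard error was 0.7/2.5/4.8/10.1% smaller. With a baseline value already in the model (correlation 0.5 within strata, effect 0.364 SD), the gain from adding age and site shrank to 0.2/0.4/0.7/1.6 points. With no strata effect it was about 0.1 points, so adjusting costs no power.

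**Dichotomous outcomes, simulated** (16,000 trials per scenario, one vitamin C arm against placebo):

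| Age odds ratio | Power, crude | Power, age-adjusted | Loss | Type I error, crude | Type I error, age-adjusted | Size-adjusted power, crude / age-adjusted |
|---|---|---|---|---|---|---|
| 1.5 | 74.4% | 74.8% | 0.3 | 4.9% | 5.0% | 74.7 / 74.8% |
| 2 | 73.0% | 73.8% | 0.8 | 4.8% | 5.3% | 73.3 / 73.1% |
| 3 | 70.2% | 72.4% | 2.3 | 4.0% | 4.7% | 73.1 / 73.0% |
| 5 | 65.0% | 70.1% | 5.1 | 3.1% | 4.6% | 71.4 / 71.4% |

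Losses were taken before rounding. At an odds ratio of 5 the crude model reports a standard error of 0.329 where the estimate's actual spread is 0.316. A smaller repeat (4,000 trials) gave 74.9 v 75.0%, 69.8 v 72.4% and 65.7 v 69.8% at odds ratios 1.5, 3 and 5. The last column shows that once both tests are set to a true 5% level the difference disappears. Adding fixed site terms gained a further 0.8 to 1.0 points, but type I error reached 5.5%.

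**Multinomial outcomes.** In simulation of a seven-level scale, the crude global test already had type I error of 5.7 to 6.3% because of sparse cells, and age adjustment raised this to 6.2 to 6.7%. The SAP plans odds ratios with intervals and names no global test, so power from such a test is not used as evidence here.

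**The case against.** The strongest case against is that this is largely a preference. The crude analysis is openly pre-specified, it is valid, and different models for primary and secondary outcomes are not a contradiction. All of that is correct. A reader might infer that ignoring the strata biases the secondary results or adds false positives. Nothing supports this: where crude type I error departs clearly from 5% in the continuous and binary models, it falls below.

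A reader might also infer that both factors are lost everywhere. The SAP does not establish that. In the primary section the word crude appears to mean without age, with site and baseline score retained. Read the same way, a secondary mixed model could still contain site. Only the loss of age is clear throughout; the absence of site is clear only for the logistic and multinomial models. That the word is undefined is a wording query and not a separate defect.

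For dichotomous outcomes the gain is only recovered conservatism, as the size-adjusted power shows. This stands. It still has a practical effect, since results will be judged by nominal 95% intervals.

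A reader might further expect a large gain for the mRS. That would rest on a global test the SAP does not plan, and adjustment would make that test slightly more liberal. This objection stands and limits the fix. It also stands that the larger losses need prognostic strengths at the top of an assumed range.

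**Conclusion.** The point holds as a minor one. The secondary tests are valid but conservative to the extent that site and age predict outcome. The loss is about 0 to 3 points for continuous outcomes without a baseline value when strata explain up to 10% of variance, and about 5 points at 20%; it is under 2 points where baseline is already adjusted for. For dichotomous outcomes it is about 0 to 2 points up to an age odds ratio of 3 and 4 to 5 at 5, all of it calibration. If age and site are weak predictors the loss is negligible. These sizes rest on assumed prognostic strength, site shares, age split and treatment effects, none of which the SAP gives. No secondary conclusion is threatened. The case for change is that analysing by the randomised strata is nearly free and would bring most secondary models into line with the primary one.

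**What to change.** Timing of final analysis says "First, the analyses will be performed with blinded data". Before that step, replace the crude rule for secondary outcomes with wording such as:

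> *Continuous secondary outcomes are adjusted for the age stratum used at randomisation and for the baseline value where measured, with a random intercept for site as in the primary model. Dichotomous outcomes are adjusted for the age stratum. The adjusted result is the main one and the crude result is shown as support. For the multinomial outcomes (mRS, CPC, oxalate crystals) the planned analysis remains the main one, and the age-adjusted result is shown as support only.*

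Naming the stratum matters because the primary section does not say whether age enters as a class or in years. State in the same edit what crude retains.

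The cost is a short SAP edit and no new data, since site and age stratum were needed to randomise each patient. There are two downsides. Adjusted odds ratios are conditional on age and not marginal, which is a different quantity and not a correction of bias. Their standard errors are also larger, by 0.7/1.7/3.8/7.9% at age odds ratios of 1.5/2/3/5. Leaving site out of the logistic models gives up 0.8 to 1.0 power points but avoids estimation in sparse sites and a slightly liberal test.

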#### Planned sensitivity analyses

Two sensitivity analyses will be carried out:

- Excluding randomized patients who died <96 hours because death at 96h was counted
  as the maximum R-SOFA score of 24 points. The choice to give 24 points to deceased
  patients may have a large impact on the primary analysis.

- Excluding randomized patients from whom the study treatment was terminated prematurely (<96 hours). For instance, this applies to patients transferred from ICU to ICU during the study period and patients fulfilling one of the 3 safety exclusion criteria.

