#### **Interim analysis**

A blinded interim analysis focused on mortality will be caried out by the trial statistician after inclusion of 135 evaluable patients. Analysis will be group comparative. The data safety monitoring board (DSMB) will be blinded but may be unblinded by the trial statistician. The DSMB can advise to stop further recruitment in case of significantly higher mortality in the

vitamin C group(s) compared to placebo and after thorough examination of the clinical content.

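### The only planned check on the 24-point death score removes everyone who died before 96 h; no planned analysis keeps all patients and tests whether the conclusion depends on the value 24

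*SAP*

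**What the plan says.** Under Primary outcome and analyses, the SAP defines the outcome as a change score: "The R-SOFA score at 96 h after randomization minus the score after ROSC (baseline R-SOFA score"). It is analysed with "linear mixed model analyses, with a random intercept on site level", adjusted for the baseline score. The age-adjusted version is primary.

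How deaths enter the outcome is stated under Planned sensitivity analyses: death by 96 h counts "as the maximum R-SOFA score of 24 points". The same section gives the reason for a check. "The choice to give 24 points to deceased" patients is acknowledged as possibly having a large effect on the primary analysis.

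The section is explicit about the number of checks: "Two sensitivity analyses will be carried out". The first is "Excluding randomized patients who died <96 hours because death at 96h was counted" as the maximum. The second is "Excluding randomized patients from whom the study treatment was terminated prematurely (<96 hours"). Neither keeps the deaths in the data and values them differently.

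**The concern.** The plan names a specific worry, the influence of one chosen number, and answers it by changing the set of patients. Death before 96 h occurs after randomisation and is part of the primary outcome. Restricting to survivors therefore selects on the outcome. If treatment changes who survives, the survivors in each arm differ in severity for reasons other than the treatment's effect on organ function.

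The plan treats a mortality difference as possible. Under Interim analysis, "The DSMB can advise to stop further recruitment in case of significantly higher mortality in the" vitamin C group or groups.

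What is at stake is interpretation. If the survivors-only result differs from the primary result, there are three possible reasons: the value 24 is influential, a real mortality effect has been left out, or the survivors are a selected group. The planned pair of analyses cannot separate these.

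**Working it through.** **1. Is the score tested anywhere else?** The additional analyses of the primary outcome add covariates and pool the vitamin C arms. The Subgroup analyses section adds interactions with age and first pH. The Missing data section expects no missing primary outcome. Survival at day 28 and day 180 is a separate secondary outcome. None of these keeps all patients and gives death another value or a rank.

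**2. Inputs.** From the SAP (Sample size; Definition of analysis population): 2-point target, 82 per group, 90% power, two-sided alpha 0.01, 90 per arm analysed. The SAP states no SD, so 82 cannot be reproduced from its own inputs. Solving backwards:

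SD = 2 × √(82/2) / (2.576 + 1.282) ≈ 3.32

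An SD of 3.30 gives n = 81.02, rounded up to 82. I use 3.3. The mortality rates, the correlation ρ between death risk and the 96-h score, and the survivor means are all assumptions.

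**3. Selection shift among survivors, with no treatment effect on any patient's own score.** Let severity be standard normal, with the sickest fraction p dying. Mean severity among survivors is −m(p), where m(p) = φ(z₁₋ₚ)/(1−p). This gives m(0.10) = 0.195, m(0.15) = 0.274, m(0.20) = 0.350, m(0.25) = 0.424 and m(0.30) = 0.497.

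Shift against the arm with fewer deaths = 3.3 × ρ × [m(p higher) − m(p lower)].

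Standard error of the survivors-only difference = 3.3 × √(1/n₁ + 1/n₂), with n = 90 × (1 − p).

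| Deaths | Shift | ρ = 0.3 | ρ = 0.9 | SE |
|---|---|---|---|---|
| 15% vs 10% | 0.26ρ | 0.08 | 0.24 | 0.53 |
| 25% vs 15% | 0.49ρ | 0.15 | 0.44 | 0.55 |
| 30% vs 20% | 0.48ρ | 0.15 | 0.44 | 0.57 |

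The shift is thus about 0.1 to 0.4 points, below one standard error throughout. It is zero if ρ = 0 or if mortality is equal between arms.

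**4. Effect of baseline adjustment.** The planned model adjusts for the baseline score; step 3 does not. In a simulation of 25% vs 15% deaths with an assumed correlation of 0.6 between baseline score and severity, adjustment lowered the shift from 0.24 to 0.18 (ρ = 0.5) and from 0.44 to 0.33 (ρ = 0.9), a reduction of about a quarter.

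**5. How much the value 24 can matter.** The part of the arm difference that comes from deaths is approximately the risk difference × (death score − survivor mean). With a 10-percentage-point mortality difference and a survivor mean of 10 or 6:

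0.10 × (24 − 10) = 1.4; 0.10 × (24 − 6) = 1.8

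against a 2-point target. Each point taken off the death score moves the estimate by 0.10; going from 24 to 20 moves it by 0.10 × 4 = 0.4.

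**6. The analyses side by side.** In a simulation with 20% vs 10% deaths, ρ = 0.5 and no effect on a patient's own score, the difference (active minus control) was −1.52 with death at 24, −1.32 at 22 and −1.12 at 20. Survivors-only gave +0.25. If treatment instead raised deaths from 20% to 30%, survivors-only gave −0.25 (ρ = 0.5) to −0.33 (ρ = 0.7), while death at 24 gave +1.58 to +1.55. These are simple differences in mean change, not the mixed model.

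**The case against.** The strongest reply is that the check does part of what it is meant to do. Removing the 24s and comparing with the primary result shows roughly how much of the effect comes from deaths. In the example in step 6 the estimate moves from −1.52 to +0.25, about 1.8 points, which no reader would miss. That stands. A reader might infer that the planned analysis says nothing about the 24-point score, and this goes too far. What it cannot show is whether the conclusion would hold under another valuation of death, and the movement it does show includes some selection.

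Second, the selection shift is conditional and small: it needs both a mortality difference and a link between death risk and score, it stays under one standard error, and baseline adjustment probably reduces it. Every mortality input is assumed. This also stands, and it limits the weight of the point.

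Third, deaths are visible elsewhere: day-28 and day-180 survival, and deaths among the serious adverse events to day 28, counted by group. This reduces the risk that the survivors-only figure is read alone, but none of these is 96-h mortality and none varies the score.

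Fourth, rerunning the model with a low death score, or with the last observed score, could rank a dead patient better than a living one. That is correct, and it favours a rank-based analysis. The detailed rationale for 24 may also lie in the published protocol, to which the SAP refers, so no criticism is made here of choosing 24.

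**Conclusion.** The point holds in a limited form. The check removes a post-randomisation component of the primary outcome. It indicates roughly what the deaths contribute, but the survivor groups may not be comparable, and no planned all-patient analysis tests dependence on the value 24.

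The possible shift against the arm with fewer deaths is about 0.1 to 0.4 points before baseline adjustment, given the mortality pairs, SD 3.3 and correlations of 0.3 to 0.9 used above. With equal 96-h mortality it vanishes, though the score would still not have been varied.

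A reader might also infer that the primary comparison is compromised. The SAP does not support that: deaths stay in the primary analysis, and the exclusion is a labelled sensitivity analysis with its reason given. This is an inexpensive improvement to a supporting analysis.

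**What to change.** Under Planned sensitivity analyses:

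- Add, for all mITT patients, a rank-based or proportional-odds analysis of the 96-h R-SOFA with death as the worst category, adjusted for baseline score and age as in the primary model where possible.
- Optionally, rerun the primary model with other fixed death scores, none lower than the highest score seen in survivors, so that no dead patient ranks better than a living one.
- Keep the survivors-only analysis, label it descriptive, and show it beside 96-h mortality in each of the three arms.
- State when the additions were made. The SAP plans a first analysis with arms coded A, B and C; anything added after unblinding should be labelled post hoc.

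The cost is SAP wording, a few runs on data already collected, and a few more results to report.
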